Because NR reduces senescence markers in aged mouse muscle (32), the frequency of p16+ nuclei, an indicator of senescence, will also be determined, as well as co-localization of p16 and Pax7. Muscle fiber type and size will be quantified with myosin heavy chain-specific antibodies as described (75), to assess overall muscle fiber phenotype in response to the interventions. The frequency of regenerating muscle fibers will also be determined using an antibody against embryonic myosin heavy chain. Additional muscle measures not specified here may be performed in [name] and in [name] laboratory, based on findings in other ongoing studies of calf skeletal muscle dysfunction in people with PAD. Measures of senescence, including P16+ cells, may be performed in fat tissue obtained during the muscle biopsy in the laboratory of [name] and/or [name] at Mayo clinic.

Other measures. Body mass index (BMI) will be assessed at baseline and follow-up by objectively measuring height and weight. A four-meter walk test will be administered at usual and fastest pace at the baseline and follow-up visits. Participants will be asked to perform the usual paced four-meter walk at usual pace and the "fast paced" four meter walk at their fastest pace. Each of these short walks will be performed twice. Participants will be asked to complete a series of standing balance tests and chair stands. Names and doses of participants' medications will be systematically recorded at baseline and at follow-up.

Microbiome. Study participants may be asked to provide a stool sample. Participants who agree to this optional element will be given supplies to swab the toilet paper after a bowel movement, place the swab into a tube labeled with their study ID number, and mail back the tube in a pre-stamped envelope within 48 hours of collection. Alternatively, the participant may be asked to bring the swab to a study visit to return in person, depending on their appointment schedule. This sample will be used to identify specific bacterial species whose relative abundance is either negatively or positively correlated with PAD and other patient characteristics, such as body mass index and PAD severity. Participants will be asked to complete a short diet and lifestyle questionnaire (self-administered or verbally completed in person or over the phone with a research study coordinator) during the week when the stool is collected. The stool sample will be mailed for analysis to the laboratory of [name], a Professor of Pediatrics and a Professor in the Center for Microbiome Innovation at the University of California San Diego. Some of the serum that is already collected as part of study blood collection procedures may be mailed to [name] laboratory for analyses of microbial metabolites.

DATA AND SPECIMEN BANKING

Muscle specimens and blood specimens for long-term storage will be stored in a freezer belonging to [name] research program at Northwestern University, in the freezer farm in the basement of Olson Pavilion. Specimens will be stored for up to 70 years, after which they will be destroyed.

Specimens will be coded; meaning that a key will exist that can link the codes back to the direct subject identifiers. Each participant will be assigned a unique study ID number that can be traced back to the study participant. The muscle specimens and the blood samples that are stored will be labeled with this unique identifier and the date and time of the blood collection.

Only [name] has control over release of study data or specimens. Any investigators seeking to analyze blood or muscle specimens must contact [name] for permission. Each request, if it occurs, will be considered on a case-by-case basis. [name] will obtain IRB approval prior to releasing any blood or muscle specimens for analysis, other than those tests specifically named in this application.

SHARING RESULTS WITH PARTICIPANTS

Participants will receive results of their ankle brachial index (ABI) test and will be provided with a “result letter” at the end of their baseline visit. ABI and stress test results will be mailed to the participant’s physician upon request. They will not be provided with other study results routinely. However, participants will be notified of medically significant stress test, blood, or blood pressure results identified in the stress test or ABI.

STUDY TIMELINES

Each participant will participate in the study for approximately six months after randomization. We plan to enroll 90 participants over an approximately three-year period. Primary analyses are anticipated to be completed by approximately April 2022.

INCLUSION AND EXCLUSION CRITERIA

Inclusion criteria. All participants will have PAD. PAD will be defined as the following: 1) An ankle-brachial index (ABI) ≤ 0.90 at the baseline study visit or 2) Vascular laboratory evidence or angiographic evidence of PAD. Inclusion based on prior vascular laboratory evidence will be determined by the study principal investigator and includes, for example, a toe brachial index (TBI) < 0.70 , Duplex measure showing 70% stenosis or greater, a post heel-rise or post-exercise ABI drop of 20% or greater, or ABI values ≤ 0.90 . Angiographic evidence of PAD consists of a stenosis of 70% or greater in a lower extremity artery.

Exclusion criteria.

1. Above- or below-knee amputation.
2. Critical limb ischemia.
3. Wheelchair-bound or requiring a walker to ambulate.
4. Walking is limited by a symptom other than PAD.
5. Current foot ulcer on bottom of foot.
6. End stage renal disease defined as a GFR less than 20 ml/min/1.73 M².
7. Significant liver impairment defined as two or more hepatic function enzymes >3.0 times the upper limit of normal. [NOTE: participants who meet this criterion may undergo a re-test of hepatic function tests to determine whether initially elevated hepatic enzymes represented a transient or spurious phenomenon.]
8. Failure to successfully complete the 2-week study run-in.
9. Planned lower extremity revascularization, orthopedic surgery, or other major surgery during the next six months.
10. Lower extremity revascularization, orthopedic surgery, cardiovascular event, coronary revascularization, or other major surgery in the previous three months.
11. Participation in supervised treadmill exercise during the previous six months.
12. Major medical illness including renal disease requiring dialysis, lung disease requiring oxygen, Parkinson’s disease, a life-threatening illness with life expectancy less than six months, or cancer requiring treatment in the previous two years. [NOTE: potential participants may still qualify if they have had treatment for an early stage cancer in the past two years and the prognosis is excellent. Participants who only use oxygen at night may still qualify.]
13. Mini-Mental Status Examination (MMSE) score <23 or dementia.
14. Participation in or completion of a clinical trial in the previous three months. [NOTE: after completing a stem cell or gene therapy intervention, participants will become eligible after the final study follow-up visit of the stem cell or gene therapy study so long as at least six months have passed since the final intervention administration. After completing a supplement or drug therapy (other than stem cell or gene therapy), participants will be eligible after the final study

follow-up visit as long as at least three months have passed since the final intervention of the trial.]

15. Currently taking a dose of 250 mg or more of nicotinomide riboside, vitamin B3, niacin. Currently taking a slow-release form of niacin. Currently taking resveratrol or has taken any these drug(s) in past six months. Participants taking a multi-vitamin will not be excluded if the dose of vitamin B3 is less than 250 mgs.
16. Increase in angina or angina at rest
17. Non-English speaking.
18. Visual impairment that limits walking ability.
19. Women who are pregnant or who are pre-menopausal will not be eligible.
20. In addition to the above criteria, investigator discretion will be used to determine if the trial is unsafe or not a good fit for the potential participant.

Potentially eligible participants will be advised that Medicare coverage for 12 weeks of supervised treadmill exercise is now available. Potential participants who have not participated in supervised treadmill exercise covered by Medicare and who desire to participate will be referred back to their physician for follow-up. These individuals may become eligible six months after they complete supervised treadmill exercise.

Vulnerable populations (fetuses, pregnant women, children, prisoners, and institutionalized persons) and adults unable to consent will not be included in the study.

PARTICIPANT POPULATION(S)

Accrual Number:	Category/Group: (Adults/Children Special/Vulnerable Populations)	Consented: Maximum Number to be Consented or Reviewed/Collected/Screened	Enrolled: Number to Complete the Study or Needed to Address the Research Question
Local	Adults 18 and older	1000	90
Study-wide	N/A		
Total:		1000	90

RECRUITMENT METHODS

Participants will be identified from among individuals with PAD who have participated previously in research conducted by [name] and/or who have expressed an interest in participating in future studies conducted by [name]. Participants who we screen for ongoing studies who may have PAD but are ineligible for that study and interested participating in a study may be screened for this study.

In addition, PAD participants may be identified from among consecutive patients diagnosed with PAD in the non-invasive vascular laboratory at Northwestern Medical Group (NMG). [name] is medical director of the non-invasive vascular laboratory at NMG and will assist with identifying potential participants from the non-invasive vascular laboratory. As director of the vascular laboratory at NMG, [name] formally reads many of the non-invasive vascular laboratory tests. He maintains all non-invasive vascular test results in his vascular laboratory.

As director of the vascular laboratory, [name] could conceivably contact the patients whose test results are maintained in his laboratory. However, [name] prefers that the contact of potential participants in studies come from the physicians referring him for testing. Lists of patients who have undergone lower extremity arterial testing in the non-invasive vascular laboratory are generated monthly and e-mailed from NMG to [name]. A research assistant will contact referring physicians of potential participants identified from the vascular laboratory via fax, phone, page, or electronic message (EPIC or e-mail), to ask for permission to contact their patient about the study. If a reply is not received within three weeks, up to five letters are mailed from [name] about the research study. We have substantial experience with our recruitment methods for our previous or ongoing studies.

We will also obtain lists of consecutive patients with a diagnosis of lower extremity peripheral arterial disease and individuals at high risk for peripheral artery disease from Northwestern's Enterprise Data Warehouse (EDW). EDW lists will be provided by an individual who is employed by the Division of General Internal Medicine who has received training and permission to obtain the lists from the EDW.

Similar methods will be used as those described above, in which the patient's physician will be contacted via fax, telephone, page, or electronic message (EPIC or email) to ask for permission to contact their patient about the study. If a reply is not received within three weeks, up to five letters are mailed from [name] about the research study. In the recruitment letters, recipients are asked to call us if they are interested in participation or if they do not want to be contacted further. Potential participants who do not call us within three weeks of the first mailed recruitment letter may be telephoned by study staff and invited to participate.

In addition, we may use newspaper, television, and radio advertising to identify potential participants for this study. We will also use brochures, flyers, or posters that we will post in relevant office practices and public areas. We may use advertising on public transportation (i.e. Chicago Transit Authority) or online advertisements.

We will obtain a list of patients who live in the Chicago area from a mass mailing company. Using this, we will send postcards to those individuals on the list. The postcards will instruct people to call a study number if they are interested.

Recruitment materials for methods referenced above will be submitted to the IRB for approval prior to their use.

We may also use CAPriCORN for recruitment. CAPriCORN is a PCORI-funded network of institutions in the Chicago area. The purpose of CAPriCORN is to assist investigators with recruitment for clinical trials. CAPriCORN has its own IRB (Chicago Area Institutional Review board - CHAIRb) and uses ICD-9 codes and the electronic health record to identify potential participants who have PAD. These patients with PAD will be mailed a recruitment letter that describes the trial and invites the patient to participate.

We may also obtain IRB approval at the University of Chicago and/or the Jesse Brown VA Medical Center to recruit patients from these medical centers. If IRB approval is obtained from U of C and JBVAMC, letters will be mailed by an approved staff member to potential patients with known PAD. Participants recruited through these methods at JBVAMC will sign a VA consent document and will undergo some study testing on-site at the VA. Study tests include questionnaires and functional performance measures.

COMPENSATION FOR PARTICIPATION IN RESEARCH ACTIVITIES

Participants will receive \$25 for completing six-month follow-up testing.

If the participant undergoes the optional muscle biopsy portion of the study, they will receive \$100 per muscle biopsy.

Participants will be given assistance and/or reimbursement for expenses related to travel such as parking, bus/train fare, taxi or rideshare (i.e. Uber/Lyft) fare, and mileage, if requested. A receipt will be required for reimbursement above \$40. Participants will be provided up to \$90 per visit for travel reimbursement. If they require the use of our taxi or rideshare service, we will estimate the fare on www.taxifarefinder.com or on the rideshare website. A one-way fare estimate must be less than or equal to \$45 (i.e. round trip of \$90) in order for the study to provide taxi service. In some instances, a participant's travel estimate may be within the \$90 limit for their first visit, but may unexpectedly increase at a later visit due to price fluctuations with Uber/Lyft. In these instances, the study will continue to provide travel to participants and pay the increased travel fare. In addition, if after randomization, a participant becomes unable to attend study visits and requires transportation such as a shared ride service in order to continue participation, then the travel service will be provided, using investigator discretion, so that the randomized participant can continue in the trial. In these cases, the amount of travel using our taxi or rideshare service may exceed \$90.

WITHDRAWAL OF PARTICIPANTS

We anticipate that participant withdrawal from the research without their consent will be infrequent. However, a potential example is if a participant develops symptoms during the study and the principal investigator feels that the symptoms could make the study unsafe for the participant to continue. In this circumstance, the participant would be advised to follow-up with his or her physician. If the participant refuses to follow-up with their physician, it may be necessary for the participant to be withdrawn without their consent.

Some participants may decide they no longer want to participate in the study intervention. These participants will still be asked to return for follow-up testing.

Participants may withdraw from the research at any time. If they decide to leave the research, they should contact the principal investigator, [name]. If they stop being in the research, already collected data may not be removed from the study database.

RISKS TO PARTICIPANTS

Risks associated with NR and resveratrol. NR has been studied in humans and no serious adverse events have been reported (19,65). Resveratrol has been tested in multiple studies of humans (44,66,76). A systematic review reported that resveratrol is generally safe with only gastrointestinal symptoms reported at high doses (i.e. > 1,000 mgs) (76). Participants will be administered questionnaires monthly to obtain data regarding any potential side effects. Safety will also be monitored by our DSMB.

Risks associated with the muscle biopsy. The muscle biopsy is associated with several potential risks. These include discomfort during the muscle biopsy procedure and for 1-2 days afterward, scarring from the muscle biopsy skin incision, bleeding (including a hematoma), and infection. Adverse effects of Lidocaine administered prior to the biopsy include pain at the injection site, allergic reaction (including swelling of the tongue or throat, wheezing, difficulty

breathing, or death), emotional excitement, and a temporarily lowered heart rate and blood pressure. However, these adverse effects of lidocaine are rare. In addition, potential participants who are asked to hold their anti-platelet therapy during the week leading up to the muscle biopsy procedure may experience a cardiovascular event related to the temporary discontinuation of the anti-platelet therapy. First, to minimize risk related to muscle biopsy, all participants undergoing muscle biopsy will receive a written handout regarding signs to watch for that may indicate wound infection. They will also be verbally instructed in this. Each participant will be instructed to call [name] immediately if any signs of infection occur. Second, permission from the participant's physician will be required before participants are asked to discontinue anti-platelet therapy. Participants will be telephoned approximately seven days after the muscle biopsy. Participants who report any complaints about their biopsy site (such as significant pain or redness) will be scheduled for an evaluation of their biopsy site by a study physician.

Risks associated with the six-minute walk test, treadmill stress test, four-meter walks, balance, and chair stands. The physical functioning tests may be associated with muscle fatigue or soreness. These symptoms typically resolve with rest. These tests may be associated with the risk of falling, irregular heartbeat, heart attack, or coronary ischemia or dyspnea due to heart failure or lung disease. Rarely, falling may result in a fracture. However, the research assistant who will collect these data has been trained to prevent falling. The risk of a fracture secondary to a fall during the testing is less than 1 in 8,000. If a participant experiences chest pain, research assistants are trained to page [name] immediately. If the chest discomfort does not immediately resolve with rest, participants are escorted to Northwestern's Emergency Department, which is located in the same building as the location of the tests. [name] facilitates follow-up as appropriate, by contacting participants' physicians, for those who experience new chest discomfort during testing, for example. In our experience, the risk of chest discomfort is approximately 1 in 750. Symptoms or results from the treadmill stress test may lead to further testing or hospitalization or recommendations for procedures to improve blood flow to the heart.

Risks associated with ABI measurement. The ankle brachial index measurement consists of measuring systolic blood pressure in each extremity using a hand-held Doppler. The ABI is non-invasive, safe and does not have any known lasting side effects. During the ankle-brachial index test, participants may experience discomfort from the inflated blood pressure cuff. However, this discomfort resolves immediately when the cuff is released.

Risks associated with questionnaire administration. Participation includes a risk of loss of confidentiality regarding personal health information. However, all research staff have undergone formal human subjects training. They are trained to protect the privacy of research subject participants.

Risks associated with drawing blood. The potential risks of drawing blood include a bruise at the site of vein puncture, inflammation of the vein, and infection. Participants undergoing a blood draw may experience lightheadedness, dizziness, or fainting.

In addition to these risks, this research may cause harm in ways that are unknown. These may be a minor inconvenience or may be so severe as to cause death.

POTENTIAL BENEFITS TO PARTICIPANTS

Participants who are randomized to receive nicotinamide riboside could experience improved functional performance or less decline in functional performance, if our hypotheses are correct.

DATA MANAGEMENT AND CONFIDENTIALITY

Data is recorded using preprogrammed instruments and an electronic case report form using secure, HIPAA-compliant REDCap database software on servers maintained by Northwestern's Clinical and Translational Sciences Institute. We have substantial experience with REDCap.

Power and Sample Size Estimation. We will enroll 30 patients per group. Based on our experience with randomized trials in PAD, we anticipate that 27 participants in each group will complete 6-month follow-up and provide outcomes for the statistical analysis (44,74). For Primary Aim 1, we will use a two-sample t-test to compare the 6-month decline in six-minute walk distance between NR alone and placebo. Twenty-seven participants per group provides 80% power for detecting a difference of 0.69 standard deviation (SD) of the decline at the one-sided significance level of 0.1. Based on our GOALS Trial results (74), a 0.58 SD represents a difference of 30 meters in six-minute walk distance. Similarly, for Primary Aim 2, we will have 80% power for detecting a difference of 30 meters between NR combined with resveratrol vs. placebo. For Secondary Aim #1 and Secondary Aim #2, we will have 80% statistical power for detecting a difference of 30 meters between the NR alone vs. placebo group (Secondary Aim #1) and between the NR combined with resveratrol group vs. the placebo group (Secondary Aim #2) at 3-month follow-up. In our Secondary Aim #3, we will have 80% statistical power for detecting a difference of 30 meters between the NR combined with resveratrol group and the NR alone group at 3-month and at 6-month follow-up. Most prior studies have defined clinically meaningful changes in the six-minute walk as 20-50 meters (77-80). Thus, the study has sufficient statistical power for detecting a clinically meaningful difference under the same assumptions. The NICE Trial is a proof of principle study intended to collect evidence for a large randomized trial. For Secondary Aim #4, we will compare changes in maximal treadmill walking distance, the WIQ distance score and physical activity between NR alone vs. placebo. The study provides 80% power for detecting a difference of 0.58 SD. Similarly, in Secondary Aim #5, we will compare changes in maximal treadmill walking distance, the WIQ distance score and physical activity between NR + resveratrol and placebo. In our GOALS trial, 0.69 SD of 6-month decline in WIQ represented a difference of 14 points for the WIQ distance score (74). The difference in reported cut-off values in WIQ scores between high and low PAD performers is 76 minus 43, or 33 points (83). Therefore, the study should have sufficient statistical power for detecting clinically important differences in the WIQ distance score. For Secondary Aim 6, we will compare 6-month changes in maximal treadmill walking distance, the WIQ distance score, and physical activity between people randomized to NR combined with resveratrol, compared to NR alone. For Secondary Aim 7, we will compare 3-month and 6-month changes in six-minute walk distance between all people randomized to an NR group (i.e. those randomized to NR combined with resveratrol and those randomized to NR alone) and those randomized to placebo. For Secondary Aim 8, we will compare 6-month changes in maximal treadmill walking time, the WIQ distance score, and physical activity between all people randomized to an NR group (i.e. those randomized to NR combined with resveratrol and those randomized to NR alone) and those randomized to placebo. In Secondary Aims #7 and #8, we have 80% power for detecting a difference of 0.50 SD. The proposed mixed effects regression analysis has a higher power than the two-sample t-test and thus can detect even smaller differences.

Statistical Analyses. Analyses will be performed using the intention to treat principle. Prior to the analyses, the distributions of the variables (changes) will be examined. For our Primary Aim #1, we will use a mixed effects repeated measurements (MMRM) regression to compare changes in six-minute walk performance at 6-month follow-up between the NR alone vs. placebo groups, adjusting for age, sex, race, and baseline six-minute walk distance. Age, sex,

and race will be adjusted for because of their association with change in six-minute walk distance (see below). Similar analyses will be performed for Secondary Aims #1, #2, #3, and #7. For our Primary Aim #2, we will use a one-tailed t-test based on MMRM to compare changes in six-minute walk between NR combined with resveratrol vs. placebo. We will perform MMRM regression analysis with the change in six-minute walk distance at month 3 and month 6 as the correlated response variable with an unstructured covariance matrix to evaluate differences in change in six-minute walk distance between the two groups in each comparison, adjusting for potential baseline confounders specified as following: baseline six-minute walk performance, age, sex, and race. The mixed effect regression would include patients missing the 6 month follow-up visit, assuming missing at random. If either primary aim is positive, the clinical trial will be considered positive. A one-sided P value at $P<0.10$ will be considered statistically significant. We are selecting this P value because of the preliminary (pilot) nature of this work. For Secondary Aims #4, #5, #6, #8 and Exploratory Aims, we will use the analysis of covariance to compare the 6-month change of each outcome, separately. In each specific comparison, the baseline value for the outcome of interest (i.e. WIQ score, treadmill, physical activity) will be adjusted for (rather than the six-minute walk) in addition to age, sex and race. For the Secondary Aims #7 and #8, the NR + placebo groups will be combined with NR + resveratrol into one group and compared to the placebo group and the MMRM regression or analysis of covariance will additionally adjust for the resveratrol usage.

For all of the analyses, The MMRM regression includes treatment indicator, visit time (month 3 and month 6 as categorical factors), the interactions between treatment and visit time, baseline six minute walking distance (for all aims in which six-minute walk is the outcome), age, sex and race. For comparisons of other endpoints not measured longitudinally, the conventional analysis of covariance will be used adjusting for the baseline level of the corresponding outcome, age, sex, and race. We will adjust for baseline six-minute walk, age, sex, and race, because these variables have been correlated significantly with either change in six-minute walk or with six-minute walk at follow-up in our prior studies. For example, in the combined data from the control groups of our GOALS, LITE, PROPEL, and TELEX randomized clinical trials of exercise interventions for people with PAD, six-minute walk at baseline was correlated with six minute walk distance at six-month follow-up (Pearson correlation coefficient= 0.812, $P<0.001$). In addition, participants who were Black had significantly poorer six-minute walk, compared to those who were not Black, at six-month follow-up (320.9 meters (SD: 104.5) vs. 359.8 meters (102.5), $P=0.0035$). Women had significantly poorer six-minute walk, compared to men, at six-month follow-up (309.6 (SD: 103.2) vs. 358.7 (SD: 102.1), $P<0.001$). In our observational WALCS cohort of men and women with PAD, older age was associated significantly with greater decline in six-minute walk distance at one-year follow-up (correlation= -0.236, $P<0.001$).

In a sensitivity analysis, we will repeat all comparisons additionally adjusting for baseline covariates that show major imbalances between relevant treatment groups, where the major imbalance is defined as Cohen's effect size being greater than 0.5. The MMRM analysis for comparing the change in six-minute walking distance will be based on all participants who have their six minute walking distance measured at least once during follow-up (i.e. at least at month 3 or month 6).

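### The detectable difference of 0.69 SD stated for Primary Aim 1 does not follow from its own inputs, which give 0.58 SD

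*Combined protocol and SAP*

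**What the plan says.** All but one of the figures are in a single paragraph, Power and Sample Size Estimation. It plans 30 per group and expects 10% loss: "we anticipate that 27 participants in each group will complete 6-month follow-up and provide outcomes for the statistical analysis". For Primary Aim 1 (NR alone against placebo) it bases power on a two-sample t-test and claims "80% power for detecting a difference of 0.69 standard deviation (SD) of the decline at the one-sided significance level of 0.1".

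The other power statements in the paragraph are:

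- The next sentence, citing the GOALS trial: "a 0.58 SD represents a difference of 30 meters in six-minute walk distance".
- For NR with resveratrol against placebo, with the same group sizes: "for Primary Aim 2, we will have 80% power for detecting a difference of 30 meters".
- For Secondary Aim #4, again NR alone against placebo: "The study provides 80% power for detecting a difference of 0.58 SD".
- For the two NR arms pooled against placebo: "In Secondary Aims #7 and #8, we have 80% power for detecting a difference of 0.50 SD".
- For the WIQ distance score, again citing GOALS: "0.69 SD of 6-month decline in WIQ represented a difference of 14 points for the WIQ distance score".

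The Statistical Analyses section confirms the significance level: "A one-sided P value at $P<0.10$ will be considered statistically significant".

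**The concern.** Primary Aim 1, Primary Aim 2 and Secondary Aim #4 all compare 27 with 27 at 80% power, so they should share one detectable standardized difference. The paragraph gives 0.69 SD for the first and 0.58 SD, directly or through 30 m, for the other two. On the plan's own scale 1 SD is 30/0.58 = 51.7 m, so 0.69 SD is 0.69 × 51.7 = 35.7 m. Read literally, the paragraph gives two detectable distances, about 36 m and 30 m, for comparisons of the same size.

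At stake is whether the power statement for a primary aim can be checked and reported. A reader could take 0.69 SD as the design effect, or infer that the trial was powered at one-sided 0.05 when it will be declared positive at one-sided 0.10. This is a proof-of-principle trial meant to inform a larger one, so the figure may be carried forward.

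**Working it through.** **Inputs.** Power and Sample Size Estimation gives a two-sample t-test, n = 27 per group, 80% power and one-sided alpha 0.10. Statistical Analyses repeats the alpha. The stated result is 0.69 SD.

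**1. Attempt to reproduce 0.69 SD.** In the normal approximation the detectable difference is

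d = (z(1−alpha) + z(power)) × √(1/n1 + 1/n2).

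With the stated inputs, d = (1.2816 + 0.8416) × √(2/27) = 2.1232 × 0.2722 = 0.578 SD. The exact t-test (noncentral t, 52 degrees of freedom) gives 0.582 SD. Neither gives 0.69.

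**2. Power at each candidate difference** (27 vs 27, one-sided 0.10). In the normal approximation, power = Φ(d/√(2/27) − 1.2816).

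| Difference | Normal | Exact t |
|---|---|---|
| 0.58 SD | Φ(2.131 − 1.282) = 80.2% | 79.7% |
| 0.69 SD | Φ(2.535 − 1.282) = 89.5% | 89.1% |

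For 80% power at 0.69 SD by the exact t-test, 20 per group would be enough (81.0%; 19 per group gives 79.4%).

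**3. Which inputs would give 0.69 SD?** Exact t, detectable difference:

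| n per group | Alpha | Power | Detectable difference |
|---|---|---|---|
| 27 | one-sided 0.10 | 80% | 0.582 SD |
| 27 | one-sided 0.10 | 90% | 0.703 SD |
| 30 | one-sided 0.10 | 80% | 0.552 SD |
| 27 | one-sided 0.05 (or two-sided 0.10) | 80% | 0.686 SD |

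Only the last row rounds to 0.69. That suggests a calculation at one-sided 0.05, but this is inference.

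**4. Is the 0.69 wrong, or the alpha?** The pooled comparison is an independent test. With 54 vs 27, √(1/54 + 1/27) = 0.2357.

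- One-sided 0.10: 2.1232 × 0.2357 = 0.500 SD (normal), 0.503 SD (exact t).
- One-sided 0.05: 0.591 SD (exact t).

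The plan states 0.50 SD, so one-sided 0.10 was used there. At one-sided 0.05 the power for 0.58 SD with 27 per group would be only 67.7%, which contradicts the 80% claimed for 30 m and for Secondary Aim #4. Every figure except 0.69 fits one-sided 0.10.

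**5. WIQ conversion.** The stated 14 points at 0.69 SD implies an SD of 14/0.69 = 20.3 points. At 0.58 SD, the figure given for that comparison, the difference is 20.3 × 0.58 = 11.8 points. Allowing for rounding, the range is 13.5/0.695 × 0.575 = 11.2 to 14.5/0.685 × 0.585 = 12.4. Both 11.8 and 14 are well below the plan's 33-point benchmark.

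**The case against.** The strongest reply is that the wrong number drives no decision. It understates what the trial can detect. The working claim, 80% power for 30 m, appears for Primary Aim 2 and Secondary Aims #1 to #3 and agrees with 0.58 SD. The planned adjusted MMRM is also said to have more power than the t-test. This is right about consequences and limits the seriousness of the point, but the sentence remains wrong for a primary aim.

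A second reply concerns the source-trial conversions, which cannot be checked here. The 30 m target depends wholly on 0.58 SD being 30 m. If 30 m had belonged to 0.69 SD, the SD would be 30/0.69 = 43.5 m and 0.58 SD about 25 m. Nothing in the documents suggests this, but the reassurance about 30 m does take the stated conversion as given.

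The WIQ part has a similar limit. The sentence reports a result from another trial and may be true as written. If only the multiple is out of date, 14 points would already be the 0.58 SD value (implied SD 14/0.58 = 24.1). The documents cannot settle this, so the 12-point value depends on a source check.

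Finally, the pooled cross-check uses a plain t-test, whereas the planned analyses for Secondary Aims #7 and #8 also adjust for resveratrol use. The check therefore shows which alpha was used in planning. It does not validate power for those analyses.

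**Conclusion.** The concern holds. With 27 per group, 80% power and one-sided 0.10, the detectable difference is 0.58 SD; the stated 0.69 SD overstates it by 0.11 SD, and power at 0.69 SD is about 89%. The documents identify 0.69 as the wrong figure, because the only stated alpha, the 30 m claim, Secondary Aim #4 and the pooled 0.50 SD all agree with one another.

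This is a reporting error in the conservative direction. The 30 enrolled and 27 evaluable per group, the one-sided 0.10 threshold, the 30 m claim and the WIQ conclusion are unchanged. The verdict rests on the plan's own t-test with equal groups and no adjustment for two primary comparisons, as the plan has it. For the metres it also takes the stated 0.58 SD = 30 m as correct. The WIQ mismatch is smaller: the multiple does not match the comparison, but the conversion is not shown to be false.

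**What to change.** In the Primary Aim 1 sentence of Power and Sample Size Estimation, change the detectable difference from 0.69 to 0.58 standard deviation.

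In the WIQ sentence, express the difference at 0.58 SD. On the implied SD of 20.3 this is about 12 points, but the sponsor should confirm the value against the GOALS data before inserting it. The 0.58 SD = 30 m conversion can be confirmed in the same look-up.

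The cost is one corrected number, one aligned conversion and a short source check. Alpha, sample size, the 30 m target and the analyses need no change.
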